5.5.2 Doses and treatment regimens

Treatment during run-in

During the run-in period (Weeks –2 [Visit 2] to Week 0 [Visit 3]) each patient will switch to study metformin and they will receive a box containing 100 tablets of 500mg and/or a box containing 56 tablets 850mg study metformin depending on individual dose metformin. Patients' initial dose of metformin will remain unchanged.

Randomized treatment period

The randomized treatment period starts at Week 0 (Visit 3) with a titration period of 4 weeks, where the patients will receive 1 double-blind kit containing either of AZD1656 starting dose of 10mg, 20mg, 20mg (fixed dose), 40mg (fixed dose), placebo, glipizide 5mg or 20mg open AZD1656. The patients will be titrated stepwise in a blind fashion to the target dose and the dose will be increased, if appropriate, weekly as they visit the clinic. Each week they will receive a new set of AZD1656 and glipizide with a higher strength. For patients in the fixed dose AZD1656 and placebo arms, the titration will be simulated and no increase in dose will take place. If a dose increase is not considered appropriate by the investigator, they will instead receive another set of IP that corresponds to the previous tolerated dose.

Randomized treatment period

After 4 weeks of titration, each patient will continue on the highest dose achieved up to 4 months as well as during the optional 2-month extension. The patients will receive a new kit of IP once a month, ie, Visit 8 and Visit 9. Patients entering the extension period will receive a new kit of IP once a month, ie, visit 10 and extension visit 12.

One kit of IP consists of:

- A wallet consisting of 1 blister of AZD1656, dose 10mg, 20mg, 40mg, 50mg, 100mg, 140mg, 200mg or placebo and a wallet consisting of a blister of glipizide 5mg, 10mg, 15mg or 20mg or placebo. Each blister card of AZD1656 will have 10 rows, where 1 row is 2 doses consisting of 2 tablets each. The glipizide blisters will also consist of 10 rows where 1 row is 2 doses consisting of 2 capsules each.

Study medication should be returned by the patients for drug accountability.

Treatment during the extension period:

The patients in the extension will continue on the same blinded (cohort 1) or open treatment (cohort 2) as during the 4 months study.

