After signing the optional genetic informed consent, a blood sample can be taken at any visit after randomization.

Visit 4 to Visit 7 (Titration period)

One week after randomization (visit 4) and thereafter one visit per week (visit 5 to visit 7) will be scheduled in the morning before dose. Patients will come in fasting. Diet and lifestyle

advice will be given at all visits. New study medication will be allocated to the patients through the IVRS/IWRS system at each visit.

The following assessments will be done: Diary compliance review, PK sampling of AZD1656 (visit 4 and visit 7), physical examination (visit 7), safety laboratory screen, ECG (visit 4 and visit 7), vital signs (BP and pulse), weight (visit 7) and concomitant medications. Additional blood samples will be taken at visit 7 such as FPG, HbA1c, Insulin, C-peptide, Lipids and CRP. Drug accountability will be recorded and new study medication will be dispensed to cover the need for the coming week. The investigator will also record if any AE occurred since the last visit.

The patients need to do a 7-point glucose assessment at home within 3 days before Visits 4, 5, 6 and 7 and register the results in the Patient Diary.

Visit 8 to Visit 10 (Maintenance period)

Patient will come for visits each month starting from 2 month after randomization (visit 8) until four months after randomization (visit 10). Patients will come in fasting and undergo a physical examination, a safety laboratory screen, ECG, vital signs (BP and pulse), weight (visit 9 and visit 10), waist and hip circumference (visit 10) and concomitant medications. Advice will be given for diet and life style during all visits. Additional blood samples will be taken at visit 10 such as Insulin, C-peptide, Lipids and CRP. Fasting plasma glucose and HbA1c will be taken at all visits. PK will be taken at visits 9 and 10. The OGTT test will be performed in a subgroup of patients at visit 10. All left over study medications need to be recorded. The investigator will also record if any AE occurred since the last visit.

The patients need to do a 7-point glucose assessment at home within 5 days before Visit 8 to Visit 10 and register the results in the Patient Diary. Patients not entering the extension period will be advised to re-start their pre-study metformin treatment during Visit 10.

Visit 12 and Visit 13 (Extension period)

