3.1.3 Treatment with AZD1656/placebo/glipizide and titration overview

The investigational products (IPs) in this study for patients in cohort 1 are the blinded, randomized treatments of AZD1656/placebo, glipizide/placebo and placebo/placebo. Patients in cohort 2 will be assigned the open treatment of AZD1656.

For patients in cohort 1, the dose of glipizide and of AZD1656 in the titrated arms will be increased stepwise on a weekly basis in a blinded fashion during the first 4 weeks after randomization. On Visits 4, 5 and 6 the dose of blinded treatment will be increased if the fasting morning plasma glucose analysed at the clinic at the specific visit is >6.1 mmol/L (110mg/dL), and no conditions (eg hypoglycaemic risk) oppose a dose increase according to investigator's judgement, See [Figure 2](#). For patients in cohort 2, the open-label dose of AZD1656 will be increased in the same way, but the increase will be open to both the investigator and the patients. See [Table 1](#) for dose steps during the titration period. Once the dose of AZD1656/glipizide/placebo is established, patients will continue on the dose achieved for the rest of the study, unless reduction is needed due to hypoglycaemia, as judged by the investigator (dose reductions will be simulated in the fixed AZD1656 arm and the placebo arm).

There will be a simulated dose increase in the placebo arm and the fixed dose arms with AZD1656.

Figure 2 Dosing overview during titration

[figure not shown]

Table 1 Schematic overview of possible daily doses of AZD1656 and glipizide during the initial titration period

	Visit 3	Visit 4	Visit 5	Visit 6
	0 = baseline	After 1 week	After 2 weeks	After 3 weeks
AZD1656 open label dose span	20mg (10mg bid)	50mg (25mg bid)	100mg (50mg bid)	200mg (100mg bid)
Randomized treatment				
AZD1656 arm higher dose span	20mg (10mg bid)	50mg (25mg bid)	100mg (50mg bid)	200mg (100mg bid)
AZD1656 arm lower dose span	10mg (5mg bid)	20mg (10mg bid)	50mg (25mg bid)	140mg (70mg bid)
AZD1656 fixed dose arm	40mg (20mg bid)	40mg (20mg bid)	40mg (20mg bid)	40mg (20mg bid)
AZD1656 fixed dose arm	20mg (10mg bid)	20mg (10mg bid)	20mg (10mg bid)	20mg (10mg bid)
Glipizide arm	5mg (5 + 0mg)	10mg (5mg bid)	15mg (10 + 5mg)	20mg (10mg bid)
Placebo arm	Placebo	Placebo	Placebo	Placebo

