5. STUDY CONDUCT

5.1 Restrictions during the study

Patients will have to comply with the following restrictions:

1. Abstain from blood and plasma donation during the study and up to 3 months after completion of the study.
2. Fast, except for water, from the night before each visit to the clinic (not applicable to Visit 2), including enrolment visit (Visit 1). During the randomized treatment period, patients should not take the IP morning dose until after arrival at clinic and after blood samples have been collected.
3. Concomitant medication: No other anti-diabetic agents than defined in the CSP according to criteria for rescue medication for hyperglycaemia are allowed during the study. However, acute treatment, up to 7 days, with any kind of insulin is allowed in all patients in acute situations, eg, infections or surgery. Treatment with certain drugs during the randomized treatment period will result in discontinuation of the patient (amiodarone, warfarin, rifampicin or potent CYP450 inhibitors, such as, but not limited to, ketokonazole and macrolide antibiotics). All other drugs will be allowed during study and changes in concomitant medications will be registered in the CRF.
4. Patients must not participate in any weight-loss programme, other than the life-style advice given according to Study Protocol, and should not initiate pharmacological weight-loss treatment during the study.
5. In case of event of suspected hypoglycaemia, patients should record the details of the event, including plasma glucose values if possible, in their Patient Diary.
6. Male patients must refrain from fathering a child during the study and for 3 months after the dose of study drug. They should not donate sperm and ensure that their partners of child bearing potential use a reliable method of contraception as well as themselves using a barrier method for this period. Acceptable methods used by female partners of child bearing potential include the oral contraceptive pill, hormonal implants, intra-uterine devices (IUDs) or diaphragms with spermicide.

Female partners should use this additional contraception for at least 3 months after the follow-up visit.

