5.5 Treatments

5.5.1 Identity of investigational products and metformin

AZD1656 and placebo will be administered as white, round tablets. The tablets will contain AZD1656 corresponding to the strength 5mg, 20mg, 50mg of the active compound respectively or placebo. The tablets will be packed into blister cards to achieve the intended dose. Each dose of AZD1656 will be composed of 2 tablets. The patient will take half of the daily dose in the morning and half of the daily dose in the evening.

Glipizide will be encapsulated into orange hard gelatine capsules and contain glipizide tablets corresponding to a dose of 5mg glipizide. The capsules will be packed into blisters of 5, 10, 15 or 20mg of glipizide or placebo. Each daily dose of glipizide will be composed of 4 capsules. When 5mg or 15mg is given as the total daily dose, the largest dose should be taken in the morning.

Patients randomized to either of the blinded arms of AZD1656 or glipizide will take two tablets AZD1656 and two capsules glipizide orally in the morning with breakfast and 2 tablets AZD1656 and 2 capsules glipizide will be administered orally in the evening with dinner. Patients fulfilling the criteria for open-label AZD1656 arm will only take two tablets of AZD1656 at each dosing event.

A wallet, consisting of a blister card of AZD1656 dose 10, 20, 40, 50, 100, 140, 200mg or placebo and a wallet consisting of a blister card of glipizide 5, 10, 15, 20mg or placebo, will be created. In total, 13 different wallet combinations will be created. AZD1656 and glipizide will be administered twice daily together with breakfast and dinner. The patient will take 2 tablets of AZD1656 and 2 capsules glipizide at each administration. Patients randomized into either of active arms of AZD1656 will take glipizide placebo and vice versa.

The number of kits to be distributed for patients receiving AZD1656 and glipizide is presented in [Table 3](#).

Table 3 Number of kits per visit for patients on AZD1656 and glipizide

Visit	AZD1656	Glipizide
2	-	-
3	1	1
4	1	1
5	1	1
6	1	1
7	4	4
8	4	4
9	4	4
10	4	4
Extension: visit 12	4	4

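### Titration visit windows allow an 11-day interval but a titration kit holds 10 days of drug, so a patient who stays in window can be one or two doses short before a fasting glucose that informs the dose step

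*Protocol*

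**What the plan says.** Four parts of the protocol bear on this.

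- **Supply.** Section 5.5.2 defines a kit as one blister of each product: "Each blister card of AZD1656 will have 10 rows, where 1 row is 2 doses consisting of 2 tablets each", and "The glipizide blisters will also consist of 10 rows where 1 row is 2 doses consisting of 2 capsules each". Table 3 in section 5.5.1, "Number of kits per visit for patients on AZD1656 and glipizide", lists one kit at each of Visits 3, 4, 5 and 6, and four kits at each later dispensing visit. Section 5.5.2 adds: "Study medication should be returned by the patients for drug accountability".
- **Visit timing.** Table 2 counts study days from day 0 and sets Visits 4 to 7 at 7, 14, 21 and 28, each ±2. Section 3.1.1 has the first of these one week after randomization and says "thereafter one visit per week (visit 5 to visit 7) will be scheduled in the morning before dose". New medication is allocated to "patients through the IVRS/IWRS system at each visit".
- **Dose decision.** Section 3.1.3: "On Visits 4, 5 and 6 the dose of blinded treatment will be increased if the fasting morning plasma glucose analysed at the clinic" exceeds 6.1 mmol/L and nothing, in the investigator's judgement, speaks against it. Section 6.3.1.3 adds home glucose data to the decision.
- **Order of events at a visit.** Section 5.1: "patients should not take the IP morning dose until after arrival at clinic and after blood samples have been collected".

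Neither a cap on the interval between consecutive visits nor a spare titration kit appears in the protocol.

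**The concern.** The windows and the kit size do not fit together for three intervals. A patient and a site who follow the protocol exactly can run out of drug shortly before a visit. At Visits 5 and 6 the glucose read at that visit is the numerical criterion for a step up.

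Section 3.2 says the glucose-lowering effect follows the plasma concentration, with half-lives of about 4 hours for AZD1656 and 12 hours for its active metabolite. A reading taken after a lapse would therefore tend to be higher than one taken on drug, and could favour an increase that was not needed. The dose reached is kept for the rest of the study unless it is reduced for hypoglycaemia (section 3.1.3), and only one such reduction is allowed (section 3.1.7). What is at stake is dosing safety in individual patients.

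**Working it through.** **Kit content.** Rows × doses per row ÷ doses per day = 10 × 2 ÷ 2 = 10 days, or 20 doses, for both products.

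**Longest in-window gap** = (later nominal day + window) − (earlier nominal day − window), with days from Table 2 and kits from Table 3:

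| Interval | Longest gap (days) | Kits | Days supplied | Shortfall (days) |
|---|---|---|---|---|
| Visit 3–4 | 9 − 0 = 9 | 1 | 10 | none |
| Visit 4–5 | 16 − 5 = 11 | 1 | 10 | up to 1 |
| Visit 5–6 | 23 − 12 = 11 | 1 | 10 | up to 1 |
| Visit 6–7 | 30 − 19 = 11 | 1 | 10 | up to 1 |
| Visit 7–8 | 65 − 26 = 39 | 4 | 40 | none |
| Visit 8–9 and each later interval to Visit 13 | 95 − 55 = 40 (same for the rest) | 4 | 40 | none |

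**Length of the lapse.** Take Visit 4 on day 5 and Visit 5 on day 16. The protocol does not say which kit supplies the morning dose on day 5, so both cases are shown.

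- *New kit:* 22 doses are needed from the morning of day 5 to the evening of day 15, and 20 are supplied. The last dose is at dinner on day 14. Two doses are missed, and the glucose on the morning of day 16 is about 36 hours after the last dose.
- *Old kit:* the new kit starts on the evening of day 5. It covers that dose (1), days 6 to 14 (18) and the morning of day 15 (1), which makes 20. One dose is missed, and the reading is about 24 hours after the last dose.

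The usual interval, dinner to the next morning, is about 12 hours. In half-lives of parent and metabolite, 12 hours is 3 and 1, 24 hours is 6 and 2, and 36 hours is 9 and 3.

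**How often.** Each visit has 5 in-window days, so each interval has 5 × 5 = 25 day pairs, and only one of them (−2 then +2) gives 11 days. An 11-day gap before Visit 5 and one before Visit 6 cannot both occur, because Visit 5 would have to be at +2 and −2 at once. Their shares therefore add. The protocol gives no visit-day distribution. Under assumed spreads, independent between visits in the first three rows:

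| Assumed spread | Share with an 11-day gap before Visit 5 or 6 |
|---|---|
| Even over the five days | 2 × 1/25 = 8.0% |
| Weights 1-2-3-2-1 | 2 × (1/9)² = 2/81 = 2.5% |
| 5% to 10% on each extreme day | 2 × 0.05² to 2 × 0.10² = 0.5% to 2% |
| Same weekday throughout | 0% |

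**Where a real step can follow.** In cohort 1 titration is real in the two AZD1656 dose spans and the glipizide arm: (90 + 90 + 90)/450 = 60%. In the placebo and fixed-dose arms it is simulated. The first, second and last rows correspond to 270 × 8.0% ≈ 22, 270 × 2.47% ≈ 7 and 0 patients in cohort 1. A full open-label cohort of 90 would add about 7, 2 and 0.

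**The case against.** The strongest reply is that little follows from the mismatch. Visits are meant to be weekly, and a 10-day kit leaves three spare days on a 7-day interval. The clinic reading is not an automatic trigger, because investigator judgement and home glucose data also enter. Fasting and bedtime readings are required daily in this period (section 3.1.2). In the example the fasting home value on day 15 is still about 12 hours after a dose, whichever kit was used. Drug accountability is recorded at every titration visit, so an empty kit would be visible when the dose is decided. A patient who was not stepped up receives the same strength again, so any leftovers still held could bridge the gap; section 5.5.2 asks for drug to be returned but does not say when. The IVRS/IWRS manual is not shown and may contain scheduling prompts or replacement kits.

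All of this stands and makes the residual risk very small. It does not close the gap. The windows define what is allowed, the protocol does not cap the interval, and it does not tell the investigator to discount a reading taken after the drug ran out.

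A reader might infer three stronger things that the documents do not support.

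- *A certain full day without drug.* Only one evening dose is missed if the earlier morning dose came from the old kit.
- *The patient shares as upper bounds.* They come from assumed spreads, and an even spread is not a maximum.
- *The size of the Table 1 steps as a measure of error.* They are the planned steps. A decision changes only if the glucose would have been 6.1 mmol/L or below on drug, is above 6.1 after the lapse, and the investigator still increases the dose. The protocol does not allow that fraction to be estimated.

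**Conclusion.** The mismatch is real and minor. In-window titration intervals can reach 11 days against 10 days of drug, which leaves the patient one or two doses short. The clinic glucose at Visit 5 or 6 is then read about 24 to 36 hours after the last dose. This happens in 1 of 25 day pairs per interval. Any share of patients, from 0% to 8.0% in the scenarios above, depends on an assumed visit-day spread and counts opportunities, not wrong steps.

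The point applies only where titration is real: the two AZD1656 dose spans, glipizide and open-label AZD1656. It assumes full adherence, return of leftovers at each visit and no replacement kit. The Visit 6–7 interval has the same shortfall, but no dose step follows and dose times are recorded for the PK samples, so nothing is argued from it. No effect on the 4-month HbA1c comparison is claimed, and none should be inferred.

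**What to change.** Keep the windows anchored to day 0, since they prevent drift. Add one footnote to Table 2: consecutive titration visits (Visits 4 to 7) must be no more than 10 days apart within the existing windows. Have the IVRS/IWRS or the site set the latest allowed date of the next visit when the kit is dispensed at the earlier visit. In the example, Visit 4 on day 5 would give day 15 as the latest date for Visit 5. A check made only when the next kit is allocated would find the lapse after it had happened.

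The cost is a footnote, a date rule and slightly less scheduling freedom. After a visit at −2 days, 4 of the 5 in-window days remain for the next visit; after any other visit day all 5 remain. No extra drug is needed, whereas an 11-row blister or a second kit at Visits 4 to 6 would also close the gap but would add supply. The cap does not help when a visit falls late and out of window; that remains a protocol deviation.

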5.5.3 Labelling

Labels will be prepared in accordance with Good Manufacturing Practice (GMP) and local regulatory guidelines. The labels will fulfil GMP Annex 13 requirements for labelling. Label text will be translated into local language.

Each wallet will be labelled with a single panel booklet label with a front page with variable text (ie, kit ID, expires end visit, E-code, daily dose (if open label AZD1656), order number and investigator). The inner pages will be country specific and translated into each language.

The labels will include the following information:

- Name, address and phone number of the sponsor (AstraZeneca).
- Dosage form, route of administration and quantity of dosage units.
- Study code.
- Kit ID.
- Direction for use.
- The name of the investigator (to be added on the label when the IP is dispensed).
- E-code (to be added on the label when the IP is dispensed).
- Storage condition.
- Batch/Lot ID number.
- Expiry date.
- The following statements:
 - “for clinical study use only”.
 - “keep out of reach of children”.

5.5.4 Storage and shipment

All study drugs should be kept in a secure place under appropriate storage conditions. The IP label on the box or wallet specifies the appropriate storage conditions. See each label for more specific information.

5.6 Concomitant and post-study treatment(s)

Other concomitant medication or therapy will be allowed during the study, from the time of signing informed consent to the follow-up visit and recorded in the appropriate section of the CRF, except for warfarin, amiodarone and potent CYP450 inhibitors such as (but not limited to) ketoconazole and macrolide antibiotics. No other anti-diabetic treatment than defined in this study protocol will be allowed. However, in addition to the defined hyperglycaemia rescue treatment described in Section 5.6.1, occasional use of insulin in case of acute illness is allowed. Such occasional use is limited to maximally 7 continuous days on 1 occasion.

Changes in concomitant medication should be avoided during study participation, with the exception of situations defined in this protocol, but medication, which is considered necessary for the patient's safety and well-being, may be given at the discretion of the investigator, who must decide if the patient should remain in study or need to be dismissed from study due to patient's safety or interference with study objectives. The administration of all medication must be recorded in the appropriate sections of the electronic case report form (eCRF) with trade names, dosages and dates of starting and ending of medication.

5.6.1 Hyperglycaemia rescue treatment

After randomisation, patients with confirmed fasting hyperglycaemia on at least 2 consecutive assessments (either SMPG measurements, samples analysed at the clinic or at the central laboratory) or an HbA1c value above 8%, should receive rescue treatment with basal night-time insulin.

The randomized treatment given to patients in **cohort 1** includes placebo and the glucose-lowering effect of AZD1656 has not been documented for periods longer than 4 weeks. Thus, criteria for hyperglycaemia requiring additional treatment with basal night-time insulin (rescue treatment) are as described below.

After randomization, hyperglycaemia will be defined in cohort 1 as follows:

- FPG greater than 15 mmol/L (270mg/dL) from baseline up to the 4-week visit (Visit 7).
- FPG greater than 13.3 mmol/L (240mg/dL) after the 4-week visit up to the 3-month visit (Visit 9).
- FPG greater than 11.1 mmol/L (200mg/dL) or HbA1c greater than 8.0 % at any time after the 3-month visit (Visit 9).

Although all patients in cohort 2 will receive active treatment with AZD1656, efficacy beyond 4 weeks is not yet documented, so criteria for hyperglycaemia requiring additional treatment with basal night-time insulin (rescue treatment) have been defined also for this cohort as described below.

After the initial titration period, hyperglycaemia will be defined in **cohort 2** as follows:

- FPG greater than 13.3 mmol/L (240mg/dL) after the 4-week visit (Visit 7) up to the 3-month visit (Visit 9).
- FPG greater than 11.1 mmol/L (200mg/dL) or HbA1c greater than 8.0 % at any time after the 3-month visit (Visit 9).

The type and brand of insulin, as well as doses used, will be according to local clinical practice and the insulin will be procured by the trial site. Initiation and subsequent dose

changes of any hyperglycaemia rescue treatment must be recorded in the appropriate sections of the eCRF.

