3.1 Overall study design and flow chart

[figure not shown]
This will be a 4-month, randomized, double-blind, placebo- and active-controlled, multi-centre study of AZD1656 as add-on therapy to metformin compared to placebo, in approximately 540 T2DM patients. Glipizide will be included in separate treatment arm as add-on treatments to metformin. After 4 months, an optional 2 months extension will follow. The study consists of 7 parallel arms with 90 patients in each arm except for the 2 fixed dose arms with AZD1656 that will consist of 45 patients in each arm.

The study includes 2 cohorts of patients, see [Figure 1](#). In the main treatment cohort (cohort 1) patients can be randomized to one of 6 different treatment arms with AZD1656, glipizide or placebo. Patients in this cohort should have HbA1c between $\geq 7.5\%$ and $\leq 10\%$ at enrolment. The patients will be randomized to 1 of 4 different dose regimens of AZD1656 (a minimum dose of 10mg daily titrated to maximum dose of 140mg daily, a minimum dose of 20mg daily titrated to a maximum dose of 200mg daily, 20mg daily or 40mg daily fixed doses), an glipizide regimen of glipizide (minimum dose of 5mg daily to a maximum dose of 20mg daily) or placebo, as add-on to an unchanged dose of metformin. The double-blind AZD1656/glipizide/placebo will be given twice daily.

Cohort 2:

In cohort 2, up to 90 eligible patients with HbA1c between $>10\%$ and $\leq 12\%$ at enrolment will be assigned (no randomization) to an open-label treatment with AZD1656, which will be titrated from 20mg up to 200mg. For safety reasons, patients in cohort 2 must meet all eligibility criteria and after the initial titration period, the same criteria for hyperglycaemic rescue medication will apply also in this cohort. Recruitment will be completed regardless of reaching the number in the open-label AZD1656 arm. The termination of the recruitment will be linked to cohort 1 (450 randomized patients).

Figure 1 Study design overview

Target patient population is T2DM patients not adequately controlled on maximum tolerated metformin dose ($\geq 1500\text{mg}$) as single therapy and with stable metformin treatment for at least 10 weeks prior to enrolment (screening).

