3.1.6 Hyperglycaemia during study

After randomization, definitions of hyperglycaemia and the use of rescue medication will apply, see Section [5.6.1](#). Patients will receive written instructions on the need for plasma glucose assessments in case of hyperglycaemia symptoms, and to contact the investigator if two consecutive fasting morning plasma glucose values are >11 mmol/L (198 mg/dL). The investigator must also at every study visit consider extra plasma glucose monitoring, especially if the patient's glucose levels start to deteriorate. Patients meeting criteria for hyperglycaemia should receive treatment with basal night-time insulin in addition to metformin and the randomized IP treatment.

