5.8 Discontinuation of investigational products

Patients may be discontinued from IP in the following situations:

1. Patient decision. The patient is at any time free to discontinue treatment, without prejudice to further treatment.
2. AE.

3. Severe non-compliance to study protocol as judged by the investigator and/or AZ/ICON Clinical Research.
4. Risk to patients as judged by the investigator and/or AZ
5. Patient lost to follow-up.
6. Incorrectly randomized patient, see Section 3.1.

Development of any study specific criteria will lead to discontinuation from IP:

- Patient uses amiodarone, warfarin, rimfampicin or potent CYP450 inhibitors, such as, but not limited to, ketokonazole and macrolide antibiotics during the study should be discontinued from the study.
- Patients who despite dose reduction of IP once, experiences more than one major hypoglycaemic event with need for external assistance due to impaired consciousness, or with other hypoglycaemic event(s) resulting in safety concerns with continued IP treatment, should be discontinued from the study. The hypoglycaemic event should be recorded in the appropriate CRF modules.
- Patients with remaining hyperglycemia despite maximum tolerable dose of basal night-time insulin, according to the investigator, should be discontinued from the study and receive appropriate glucose corrective treatment. For the definition of hyperglycemia at different time points during study, see section 5.6.1
- Patient who develops a condition contraindicating treatment with metformin or glipizide during the study should be discontinued. Conditions include, but are not limited to, renal impairment with GFR <60 ml/min, shock and diabetic ketoacidosis. However, temporary discontinuation of metformin and/or IP (up to 7 days) due to e.g. acute illness or radiological investigations with iodinated contrast media is allowed
- Increase in plasma CK levels to more than 10 x ULN on two consecutive measurements that cannot be ascribed to a benign condition or situation.
- Increase in AST and or ALT to more than 5 x ULN
- ALT or AST more than 3 x ULN and total bilirubin more than 1.5 x ULN.

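### The opening sentence of section 5.6.1 lets an HbA1c above 8% trigger rescue insulin at any time after randomization; the cohort definitions below it allow this only after Visit 9

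*Protocol*

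**What the plan says.** Section 5.6.1 of the protocol contains two statements of when rescue insulin is due.

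- **Opening sentence.** It applies after randomization to both cohorts. Its first limb is fasting hyperglycaemia confirmed on at least two consecutive assessments, with no cut-off given. Its second limb is complete in itself: "or an HbA1c value above 8%, should receive rescue treatment with basal night-time insulin".
- **Cohort definitions.** For cohort 1, the first period (baseline to Visit 7) uses FPG above 15 mmol/L. The second is "FPG greater than 13.3 mmol/L (240mg/dL) after the 4-week visit up to the 3-month visit (Visit 9"). The third is "FPG greater than 11.1 mmol/L (200mg/dL) or HbA1c greater than 8.0 % at any time after the 3-month visit (Visit 9"). Cohort 2 has no criterion before Visit 7; its later two periods carry the same limits as cohort 1. HbA1c appears only in the last period in either cohort.

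Other text points to the definitions. Section 5.6.1 says of cohort 1 that the "criteria for hyperglycaemia requiring additional treatment with basal night-time insulin (rescue treatment) are as described below". Section 3.1.6 says that "definitions of hyperglycaemia and the use of rescue medication will apply" and refers to 5.6.1. Section 5.8 adds: "For the definition of hyperglycemia at different time points during study, see section 5.6.1". For cohort 2, section 3.1 says that "after the initial titration period, the same criteria for hyperglycaemic rescue medication will apply also in this cohort".

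HbA1c is sampled at Visits 7, 8, 9 and 10 (Table 2; section 6.3.1.1). Rescue does not stop study treatment: "Patients meeting criteria for hyperglycaemia should receive treatment with basal night-time insulin in addition to metformin and the randomized IP treatment" (section 3.1.6).

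**The concern.** Both statements instruct the investigator, and they disagree for the same patient. Take a cohort 1 patient with HbA1c 8.5% at Visit 7 and FPG below the cut-off. The opening sentence says start basal insulin; the definitions say do not.

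What would be at stake:

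- **Primary comparison.** The primary variable is HbA1c change to 4 months (section 12.2.6.1). Insulin started early is more likely where HbA1c stays high, which means more often on placebo if AZD1656 works. It would lower the later values there and tend to shrink the difference from placebo.
- **Interim visits.** HbA1c change is also analysed at months 2 and 3 (section 12.2.6.2), and insulin started at Visit 7 would affect both.
- **Cohort 2.** The exploratory objective on glucose control in severely impaired patients (section 2.3) would be confounded with insulin.
- **Protocol adherence.** Section 5.6 permits only the anti-diabetic treatment that the protocol defines, apart from short acute insulin use. Section 12.1.1 counts disallowed medication as a major deviation. Insulin for HbA1c 8.5% at Visit 7 is required by one statement and arguably disallowed by the other.

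**Working it through.** The plan states no figure on this point, so there is none to reproduce. The check sets the two rules against the visit schedule.

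**Inputs.** Visit days and windows and the HbA1c row come from Table 2. The rules come from section 5.6.1, and the entry limits from section 4.1 (cohort 1: 7.5% to 10%; cohort 2: above 10% to 12%).

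**Step 1: the rules by visit.** The gap is the day of Visit 10 (120 ± 5) minus the day of the visit. The shortest gap uses 115 and the latest permitted day; the longest uses 125 and the earliest.

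| Visit | Day | HbA1c > 8%, opening sentence | HbA1c > 8.0%, definitions | Nominal gap (days) | Gap with windows (days) |
|---|---|---|---|---|---|
| 7 | 28 ± 2 | Insulin | No trigger | 120 − 28 = 92 | 115 − 30 = 85 to 125 − 26 = 99 |
| 8 | 60 ± 5 | Insulin | No trigger | 120 − 60 = 60 | 115 − 65 = 50 to 125 − 55 = 70 |
| 9 | 90 ± 5 | Insulin | Not settled | 120 − 90 = 30 | 115 − 95 = 20 to 125 − 85 = 40 |

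**Step 2: Visit 9.** The definitions apply the HbA1c criterion at any time after Visit 9. If the date of sampling decides, the Visit 9 sample does not qualify. If the date of the result decides, it may: section 12.2.7.5 says that clinical laboratory tests are done centrally, so the value would normally arrive after the visit. Before Visit 10, the opening sentence therefore gives 3 scheduled samples that can trigger rescue, and the definitions give 0 or 1. Two visits conflict on either reading.

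**Step 3: which patients the literal rule could reach.**

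- Cohort 1: the part of the entry range above 8% is 10 − 8 = 2.0 points out of 10 − 7.5 = 2.5. This is a width, not a share of patients, because the protocol gives no entry distribution.
- Cohort 2: to avoid insulin at Visit 7, a patient entering just above 10% would need a fall of more than 10 − 8 = 2.0 points by day 28. One entering at 12% would need 12 − 8 = 4.0.

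**Step 4: which rule is intended.** The FPG limb of the opening sentence cannot be applied without the definitions, and sections 3.1, 3.1.6 and 5.8 all rely on criteria or definitions that vary by period or cohort. No text outside 5.6.1 supports an untimed HbA1c trigger. The definitions are the intended rule. Nothing, however, limits the HbA1c limb of the opening sentence, which has its own threshold and action.

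**The case against.** The strongest reply is that the opening sentence is only a lead-in. The FPG limb omits its cut-off and its period; the HbA1c limb merely omits its period, and its 8% is the same threshold that the definitions use. The literal reading would also make the graded FPG limits (15, 13.3, then 11.1 mmol/L) largely pointless, since cohort 1 may enter at up to 10% and all of cohort 2 enters above 10%. Site staff are trained on the protocol (section 9.2), and no effect on the estimate has been shown.

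Most of this stands. It settles what was intended and makes the literal reading less likely. It does not correct the sentence: a reader must look up the definitions to use the FPG limb, but can act on the HbA1c limb without them.

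Two stronger readings are tempting, and the documents support neither.

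- A reader might infer that the definitions let no scheduled HbA1c sample before Visit 10 trigger rescue, giving a clean contrast of three samples against none. The wording leaves the Visit 9 sample open.
- A reader might infer that a large share of patients will be on insulin from Visit 7 and that the primary result is compromised. The protocol gives neither the entry distribution nor the expected course of HbA1c by visit, and the adjacent definitions direct sites otherwise.

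**Conclusion.** The inconsistency is real and should be fixed. The opening sentence of section 5.6.1 is wrong as written, and the timed cohort definitions are evidently the intended rule. The conflict is certain at Visits 7 and 8, nominally 92 and 60 days before the endpoint, and open at Visit 9, nominally 30 days before.

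The effect on the result cannot be derived from the protocol. It depends on how many sites apply the sentence literally, and it is nil if none do. The expected direction, a smaller AZD1656-placebo difference, rests on two assumptions: that AZD1656 lowers HbA1c, so that more placebo patients stay above 8%, and that values after rescue enter the primary analysis. Section 12.2.6.1 states no exclusion of such values, though an analysis plan not seen here might. In either case, uneven starts of insulin across about 130 centres could not be undone by analysis.

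**What to change.** Let the timed, cohort-specific definitions govern, in three steps:

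1. Replace the opening sentence with one that defers to them, for example: *Basal night-time insulin should be started as rescue in any patient who meets the hyperglycaemia definition given below for that cohort and period. FPG criteria must be confirmed on at least two consecutive assessments; HbA1c above 8.0% counts only under the post-Visit 9 criterion.* This keeps the two-assessment requirement, which the definitions themselves do not repeat.
2. State whether the sample drawn at Visit 9 counts under that criterion. Restricting HbA1c to the period after Visit 9 does not answer this by itself.
3. Notify sites.

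The cost is a short text correction, a one-line clarification and a site letter. No procedure, sample size or significance level changes.
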